8.3. Study Periods, Study Completion, and End of Trial

Terms used to describe the periods during the study are defined below:

- **baseline:** begins when the ICF is signed and ends at the first study treatment (or at discontinuation, if no treatment is given)
- **study period:** begins at the first study treatment and ends at study completion. The study period does not include the continued access period.
 - **study treatment period:** begins at the first study treatment and ends when the patient and the investigator agree that the patient will no longer continue study treatment. The date of this agreement is to be reported on the case report form (CRF) as the Date of Discontinuation from study treatment..
 - **postdiscontinuation follow-up period:** begins the day after the patient and the investigator agree that the patient will no longer continue study treatment.
 - **short-term follow-up:** begins the day after the patient and the investigator agree that the patient will no longer continue study treatment and lasts approximately 30 days.
 - **long-term follow-up:** begins the day after short-term follow-up is completed and continues until the patient's death or overall study completion.
- **continued access period:** begins after study completion and ends at the end of trial. During the continued access period, patients on study therapy who continue to experience clinical benefit may continue to receive study therapy until 1 of the criteria for discontinuation is met. The continued access period includes continued access follow-up.
 - **continued access follow-up:** begins 1 day after the patient and the investigator agree that the patient will no longer continue treatment in the extension period and lasts approximately 30 ± 6 days
- **study completion:** begins following the final analysis/evaluation of OS, as determined by Lilly. Investigators will continue to follow the Study Schedule for all patients until notified by Lilly that study completion has occurred.
- **end of trial:** occurs after study completion and after the last patient has discontinued study treatment and completed continued access period follow-up (if applicable).

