Abbreviations: CT = computed tomography; CTCAE = Common Terminology Criteria for Adverse Events; ECG = electrocardiogram; ECOG = Eastern Cooperative Group; MRI = magnetic resonance imaging; PD = pharmacodynamic; PET-CT = positron emission tomography-computed tomography; PK = pharmacokinetic; T-ALL = T-cell acute lymphoblastic leukemia; T-LBL = T-cell lymphoblastic lymphoma.

- a LY3039478 is to be administered 3 days per week through each 28-day cycle. If assessments associated with a dose cannot be performed, the assessments may be performed either with the previous dose (if known in advance) or the next dose.
- b Per protocol Section 10.1.1. To be done for only those patients who had lesions at the their baseline assessment.
- c For complete details, see [Attachment 3](#).
- d For central versus local laboratories refer to [Attachment 2](#).
- e Predose any time <28 days prior start of study drug and per protocol Section 10.4.2 postdose as clinically determined by investigator.
- f For confirmation of CR and when clinically indicated by investigator; per protocol Section 10.1.1.

Study Schedule, Protocol I6F-MC-JJCB: Phase 2

Study Procedures	Cycle 1																			
	Week 1					Week 2					Week 3					Week 4				
	Day 1	Day 2	Day 3	Day 4	Day 5	Day 8	Day 9	Day 10	Day 11	Day 12	Day 15	Day 16	Day 17	Day 18	Day 19	Day 22	Day 23	Day 24	Day 25	Day 26
LY3039478 therapy ^a or Placebo	X		X		X	X		X		X	X		X		X	X		X		X
Dexamethasone	X	X	X	X	X						X	X	X	X	X					
Physical exam	X										X									
Vital signs (temperature, pulse rate, blood pressure)	X											X								
Weight	X																			
ECOG Performance Status	X											X								
CTCAE version 4.0 grading	X											X								
Concomitant medications	X											X								
CT/MRI thorax and at least upper abdomen for T-ALL patients ^b																				X
Central ECG ^c	X																			
Hematology ^d	X											X								
Serum chemistry ^d	X											X								
ECG chemistry ^{c,d}	X																			
Coagulation ^d	X											X								
Blood PK sampling ^c	X											X								
Tumor biopsy, T-LBL optional ^e																				X
Bone marrow biopsy and/or aspirate ^f																				X
FACT-Leu																				X
Resource utilization																				X

Study Procedures	Cycle 1																			
	Week 1					Week 2					Week 3					Week 4				
	Day 1	Day 2	Day 3	Day 4	Day 5	Day 8	Day 9	Day 10	Day 11	Day 12	Day 15	Day 16	Day 17	Day 18	Day 19	Day 22	Day 23	Day 24	Day 25	Day 26

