Attachment 2. Protocol I6F-MC-JJCB Clinical Laboratory Tests

Clinical Laboratory Tests

Hematology^{a,b} with manual differentiation:

Hemoglobin
Hematocrit
Erythrocyte count (RBC)
Mean cell volume (MCV)
Mean cell hemoglobin concentration (MCHC)
Leukocytes (WBC)
Neutrophils, segmented
Neutrophils, bands
Lymphocytes
Monocytes
Eosinophils
Basophils
Metamyelocytes
Myelocytes
Promyelocytes
Blasts
Atypical lymphocytes
Platelets
Nucleated RBCs (NRBC)/100 WBC
Reticulocytes

Urinalysis^{a,c}:

Specific gravity
pH
Protein
Glucose
Ketones
Blood
Urine leukocyte esterase

Immunophenotyping Lymphocyte panel in peripheral blood and bone marrow^a:

TdT, CD1a, CD2/3/4/5/7/8/11b/13/33/34/65/117,
cCD3, HLA-DR, % of lymphoblasts in bone marrow

Coagulation^b:

D-dimer
PTT
PT/INR
Fibrinogen
Antithrombin

Clinical Chemistry^{a,b}:

Serum Concentrations of:

Sodium
Potassium
Phosphorus
Magnesium
Chloride
Total bilirubin
Direct bilirubin
Alkaline phosphatase
Alanine aminotransferase (ALT)
Aspartate aminotransferase (AST)
Lactate dehydrogenase (LDH)
Gamma-glutamyl (GGT)
Blood urea nitrogen (BUN) or blood urea
Creatinine
Uric acid
Calcium
Glucose, random
Albumin
Total protein
Lipase

Other:

Immunoglobulins G, A, and M (IgG, IgA, IgM)^{b,c}
High-sensitivity C-reactive protein (hsCRP)^{b,d}
HTLV^{b,c}

Pregnancy Test (females only)^{a,c}

Cerebrospinal Fluid^a

Leukocytes (WBC)
Lymphoblasts

ECG Chemistry^b

Lipase^e
Thyroid stimulating hormone (TSH)
Tri-iodothyronine (T3)
Thyroxine (T4)
Albumine
Glucose, random^e
Calcium

Bone Marrow^{a,b,f} with manual differentiation:	Sodium ^e
Aspirate	Potassium ^e
Core biopsy	Phosphorus ^e
	Magnesium ^e
	Serum creatinine ^e

Abbreviations: CBC = complete blood count; ECG = electrocardiogram; HTLV = Human T-cell leukemia virus type 1; M/E = myeloid/erythroid; PT/INR = international normalized ratio of prothrombin time; PTT = partial thromboplastin time; RBC = red blood cells; WBC = white blood cells.

a Local or investigator-designated laboratory.

b Assayed by Lilly-designated laboratory.

c Performed at baseline only.

d To be performed with each chemistry panel.

e Test not performed if both chemistry and ECG chemistry required at same time point. See [Attachment 3](#).

f Including Lilly-designated laboratory assessment of minimal residual disease (MRD) to confirm remission status.

**Attachment 3. Protocol I6F-MC-JJCB Pharmacokinetic,
Pharmacodynamic, CSF and ECG Sampling Schedule**

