PK, PD, CSF, and ECG Sampling Schedule – Phase 1– Part A (Adult Patients)

PK Sample Number	Cycle	Day	PK Sampling Time for LY3039478 ^a	PK Sampling Time for Dexamethasone ^a	CSF Sampling Time for LY3039478 ^b	PD Sampling Time for A β (1-x)] ^c	PD Sampling Time for NICD and Gene Expression Analysis ^{d,e,f}	ECG and ECG Chemistry
1	1	1	Predose	Predose		Predose	Predose	Predose
2	1	1	1-2h	1-2h		1-2h		
3	1	1	3-4h	3-4h		3-4h		3-4h
4	1	1	6-8h	6-8h		6-8h	6-8h	
5	1	1	24-30h	24-30h		24-30h		24-30h
6	1	8	Predose				Predose	
7	1	8	1-2h		1-4h			
8	1	8	3-4h					
9	1	8	6-8h				6-8h	
10	1	8	24-30h					
11	2	1	Predose					Predose

Abbreviation: CSF = cerebrospinal fluid; ECG = electrocardiogram; NICD = Notch intracellular domain; PD = pharmacodynamic; PK = pharmacokinetic.

^a Samples of approximately 3 mL of whole blood will be collected for measurement of LY3039478 and dexamethasone on Cycle 1 Day 1 only. On other days, 2 mL of whole blood will be collected for measurement of LY3039478.

^b Optional and only for Phase 1 adult patients.

^c Samples of approximately 3 mL of whole blood will be collected.

^d For the NICD ELISA, approximately 8 mL of whole blood will be collected in sodium citrate CPT tubes.

^e For the gene expression analysis, approximately 2.5 mL of whole blood will be collected.

^f NICD collection will be performed at select sites only.

Note: Collection of PD samples, where similar intervals are presented, should be collected the same time as PK samples. Collection of CSF sample should be at the same time as either the 1-2h or 3-4h plasma PK sample.

PK, PD, and ECG Sampling Schedule – Phase 1- Part B (Pediatric Patients)

PK Sample Number	Cycle	Day	PK Sampling Time for LY3039478 ^a	PK Sampling Time for Dexamethasone ^a	PD Sampling Time for NICD and Gene Expression Analysis ^b	ECG and ECG Chemistry
1	1	1	Predose	Predose	Predose	Predose
2	1	1	1-3h	1-3h		1-3h
3	1	1	6-8h	6-8h	6-8h	6-8 h
4	1	8	Predose		Predose	Predose
5	1	8	1-3h		3h	

Abbreviation: ECG = electrocardiogram; NICD = Notch intracellular domain; PD = pharmacodynamic; PK = pharmacokinetic.

^a Samples of approximately 2 mL of whole blood will be collected for measurement of LY3039478 and dexamethasone (where assayed).

^b NICD collection will be performed at select sites only.

Note: Collection of PD samples, where similar intervals are presented, should be collected the same time as PK samples.

PK, PD, and ECG Sampling Schedule – Phase 2 (Approximately 30 Patients)

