PK Sample Number	Cycle	Day	PK Sampling Time for LY3039478/ Placebo ^b	PK Sampling Time for Dexamethasone ^b	PD Sampling Time for NICD and Gene Expression ^c	ECG ^a and ECG Chemistry
1	1	1	Predose	Predose	Predose	Predose
2	1	1	1-3h	1-3h		1-3h
3	1	1	6-8h	6-8h	6-8h	
4	1	15	Predose	Predose		
5	1	15	1-3h	1-3h		
6	1	15	6-8h	6-8h		
7	2	1	Predose			Predose

Abbreviation: ECG = electrocardiogram; NICD = Notch intracellular domain; PD = pharmacodynamic; PK = pharmacokinetic.

a ECG required for all patients.

b Samples of approximately 3 mL of whole blood will be collected for measurement of LY3039478 and dexamethasone in Cycle 1 only. On other days, 2 mL of whole blood will be collected for measurement of LY3039478.

c NICD collection will be performed at select sites only.

Note: Collection of PD samples, where similar intervals are presented, should be collected the same time as PK samples.

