**Table JJCB.6.1. Data Definitions and Rules**

Term	Definitions or Rule
Entered	Patients who have signed the informed consent document directly.
Screen failures	Patients who have signed informed consent, do not meet eligibility criteria and are not randomized.
Randomized/ Enrolled	Patients who have been assigned to study treatment and but may have not received any study treatment (LY3039478, LY3039478-matched placebo, or Dexamethasone).
Patients on therapy	Patients who have been randomized/enrolled to study treatment and have received at least 1 dose of study treatment (LY3039478, LY3039478-matched placebo, or Dexamethasone).
Study day	If assessment is on or after date of first LY3039478/ LY3039478-matched placebo dose then (date of assessment) – (date of first study treatment dose) + 1 If assessment precedes first treatment dose then (date of assessment) – (date of first study treatment dose) There is no study day 0. Study day 1 is the date of first dose and study day -1 is the day before the first dose.
Cycle day	If assessment is on or after date of first LY3039478/ LY3039478-matched placebo dose then (date of assessment) – (date of first study treatment dose in cycle) + 1 If assessment precedes first treatment dose then (date of assessment) – (date of first study treatment dose in cycle) There is no cycle day 0. Cycle day 1 is the date of first dose in the cycle and cycle day -1 is the day before the first dose.
Baseline	For change from baseline analysis, baseline value is defined as the last reported measure on or before the first dose date (or discontinuation, if no treatment is given).
Study treatment period	Time from treatment start to when the patient and the investigator agree that the patient will no longer continue study treatment. The date of this agreement is to be reported on the case report form (CRF) as the Date of Discontinuation from study treatment.
Post-discontinuation – short-term follow-up	The short term follow-up period begins 1 day after discontinuation of study treatment and lasts approximately 30 days (Visit 801).
Post-discontinuation – long-term follow-up	The long-term follow-up period begins 1 day after the short-term follow-up period (Visit 801) is completed and continues until patient's death or overall study completion

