#### **6.14.4. Clinical Laboratory Evaluation**

Listings of all laboratory results will be provided (using SI units [International System of Units], when available) by treatment, for hematology, chemistry, urinalysis, ECG chemistry, immune phenotype, coagulation, CSF and bone marrow. Normal reference ranges, percent of the result outside of range (result divided by lower limit if result is less than lower limit; result divided by higher limit if result is greater than higher limit) and percent change from baseline will also be included. Selected laboratory parameters may be plotted by time.

Laboratory analytes below/above quantifiable levels (data in the database recorded as “ $<x$ ” and “ $>x$ ”) will be reported as such in listings, and imputed to the lower or upper limit of quantification in any summarise or analyses.

Neutrophils, platelets, lymphocytes, monocytes, eosinophils, basophils, RBC, WBC, Nucleated RBCs (NRBC)/100 WBC blasts and other laboratory parameters of interest to disease status will be plotted by time. Data will be log transformed and the logged ratio to baseline analysed by mixed effect model repeated measures with treatment, cycle, and the interaction of treatment and cycle as fixed effects, with baseline and the interaction of baseline and cycle as a covariate. An unstructured variance covariance matrix will be used, data permitting. Otherwise, the following variance covariance structures will be tested and that with the best fit according to AIC selected: compound symmetry, heterogeneous Toeplitz, first-order autoregressive combined with random patient effect, heterogeneous autoregressive, or heterogeneous compound symmetry. The Kenward-Roger method will be used to estimate denominator degrees of freedom. Geometric means and treatment comparisons with corresponding 95% confidence intervals (CIs) for each cycle will be presented in tabular and graphical displays.

A waterfall plot will be provided for minimum percentage bone marrow blasts by treatment arm, coloured by gene mutation status.

A calculated CTCAE grade using CTCAE v4.0 (or higher) will be provided for all laboratory results which can be used independently of clinical judgment to determine a CTCAE severity grade.

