#### **6.14.6. Electrocardiograms**

Electrocardiogram (ECG) assessment of normality and clinical significance will be listed by treatment group. Myocardial information and quantitative results including PR, QRS, QTcB (Bazett's correction), QTcF (Fridericia's correction) and RR intervals will be provided in patient listings for absolute and change from baseline. In addition, summaries of outlying corrected QT intervals (QTc, QTcB and QTcF) will be provided by treatment. Outlying intervals include absolute values  $> 450$ ,  $> 480$  and  $> 500$  msec and change from baseline  $> 30$  and  $> 60$  msec.

Further exploratory analyses may be conducted as warranted.

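### The SAP sets baseline by date alone, so a post-dose ECG from Cycle 1 Day 1 can become the reference for the QTc change counts (minor, descriptive safety outputs only)

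*SAP*

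**What the plan says.** SAP section 6.1, Table JJCB.6.1, gives one baseline rule for all change-from-baseline work: the "baseline value is defined as the last reported measure on or before the first dose date". The same table makes the date of first dose study day 1. The rule mentions neither clock time nor a predose label.

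Two outputs that use this baseline concern assessments repeated on the dosing day:

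- SAP 6.14.6 lists ECG intervals as absolute values and as change from baseline. It adds that "summaries of outlying corrected QT intervals (QTc, QTcB and QTcF) will be provided by treatment", where outlying means absolute values above 450, 480 and 500 msec and changes above 30 and 60 msec.
- SAP 6.14.4 lists laboratory results, ECG chemistry among them, and says that "percent change from baseline will also be included".

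Neither section sets its own baseline.

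The three Protocol Attachment 3 schedules each have a column covering "ECG and ECG Chemistry" (the Phase 2 heading adds a footnote letter). Each shows a predose entry and at least one post-dose entry on Cycle 1 Day 1. The Phase 2 table is headed as covering about 30 patients, but its footnote says "ECG required for all patients".

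Protocol 8.3 defines the baseline study period as one that "begins when the ICF is signed and ends at the first study treatment".

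**The concern.** A change from baseline in a safety table should compare an on-drug value with a pre-drug value. A rule that stops at the dose date, not at the dose, admits anything recorded later that day. If the last Day 1 ECG is post-dose, two things follow. That ECG's own change is never counted, because it has become the reference. And any acute shift it carries is subtracted from every later change.

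The counts above 30 and 60 msec are the part of the QTc summary that compares each patient with their own reference. If LY3039478 had an acute effect on QTc, the error would reduce the counts for patients receiving it, and in Phase 2 only in the active arm. That is the non-conservative direction for a safety display.

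The laboratory issue is separate. A same-day post-dose ECG-chemistry result can become the baseline for that analyte's percent-change listing.

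**Working it through.** The plan states no figure to reproduce, so the check applies the rule to the schedule.

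**Step 1: which ECG does the rule select?** The inputs are the Table JJCB.6.1 rule and the ECG column of Attachment 3.

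| Part | ECGs on Cycle 1 Day 1 rows | Later ECG in Attachment 3 | Baseline under the rule, if post-dose ECGs fall on the dose date |
|---|---|---|---|
| Part A | predose, 3-4h, 24-30h | Cycle 2 Day 1 predose | 3-4h |
| Part B | predose, 1-3h, 6-8h | Cycle 1 Day 8 predose | 6-8h |
| Phase 2 | predose, 1-3h | Cycle 2 Day 1 predose | 1-3h |

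The Part A 24-30h record always falls after the dose date.

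**Step 2: when is the date condition met?** A record is certain to share the dose date if dose time plus the end of its window falls before midnight:

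- 1-3h: dose before 24:00 - 3 h = 21:00
- 3-4h: dose before 24:00 - 4 h = 20:00
- 6-8h: dose before 24:00 - 8 h = 16:00

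In Part B, a dose between 16:00 and 21:00 can push the 6-8h record past midnight, but the 1-3h record is still post-dose and still becomes baseline. The documents fix no clock time for dosing, but only evening dosing avoids the problem in every part.

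**Step 3: how many scheduled change values remain?** This counts Attachment 3 ECGs after the reference.

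| Part | Predose reference | Rule as written | Same-day post-dose changes |
|---|---|---|---|
| Part A | 3 (3-4h, 24-30h, Cycle 2 Day 1) | 2 | 1 to 0 |
| Part B | 3 (1-3h, 6-8h, Day 8) | 1 | 2 to 0 |
| Phase 2 | 2 (1-3h, Cycle 2 Day 1) | 1 | 1 to 0 |

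In Phase 2 the 1-3h ECG is the only one Attachment 3 places after a dose on the same day. Under the rule it is never compared with a pre-drug value.

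**Step 4: effect on the Phase 2 count above 30 msec with no drug effect.** The planned active arm is 40 patients (Protocol 12.1). The following are assumptions, not in the documents: independent normal errors with within-patient SD s of 6 to 10 msec per ECG.

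- Rule as written, one remaining comparison: expected count = 40 × [1 - Φ(30 / (s√2))]. For s = 10: 30/14.14 = 2.12, tail 0.0169, count 0.68. For s = 6: 30/8.49 = 3.54, tail 0.0002, count 0.01.
- Predose reference, two comparisons sharing one baseline error b: expected count = 40 × [1 - ∫ Φ((30 + b)/s)² f(b) db], with f the normal density with SD s. For s = 10 this is 1.25; for s = 6 it is 0.02.

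The difference is 1.25 - 0.68 = 0.57 patients in 40 at s = 10, and 0.02 - 0.01 = 0.01 at s = 6. That is at most about 0.6.

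**Step 5: direction if there is an effect.** If QTc is shifted by D at the Day 1 post-dose ECG, and by a later residual R, the expected later change is R under a predose reference and R - D under the rule. Whenever D is above zero the rule lowers the count.

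**Step 6: ECG chemistry.** Attachment 1 marks serum chemistry and ECG chemistry on Cycle 1 Day 1. Attachment 2 footnote e says of the analytes it marks: "Test not performed if both chemistry and ECG chemistry required at same time point". Their predose value may therefore sit in the serum panel, leaving the post-dose draw as the last Day 1 record. The same date rule then makes that draw the baseline for the percent-change listing.

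**The case against.** The strongest reply is that the intent is plain. Protocol 8.3 ends the baseline period at first treatment, and the SAP entry carries almost the same proviso for untreated patients. Attachment 3 labels the first Day 1 ECG as predose, and SAP 6.14.2 refers to the time before first dose when defining treatment-emergent events. A programmer reading these together would probably choose the predose record. That stands as evidence of what was meant. It does not change what Table JJCB.6.1 says, and nothing in the SAP requires the better reading.

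A reader might go further and say the SAP contradicts Protocol 8.3 or its own adverse-event definition. The documents do not support that. One defines a study period, one classifies events, and the SAP table defines an analysis value. They show intent rather than conflict.

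The reply is also right that the consequence is limited. SAP 6.14.6 writes no between-arm ECG test. Absolute values are listed, so the true change can be recovered by subtraction. Protocol 10.3.2 has a site physician review ECGs as they are taken, independently of the SAP derivation.

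Finally, a reader might infer a large loss of QTc signals. Under the Step 4 assumptions with no later residual, a shift of 20 msec over two cycles would give 4.8-9.8 expected patients above 30 msec with a predose reference and about 0 under the rule. No document supports a shift of that size. Protocol 5.1.5 expects no hERG-related QT risk and reports no ECG effect in dogs. Such figures show direction only and should not set the severity.

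**Conclusion.** The rule is wrong as written, and the error is minor. Followed literally, it makes a same-day post-dose ECG the reference for the ECG change listings and the QTc change counts in all three study parts, provided the record falls on the dose date. On the Attachment 3 schedule this removes 1, 2 and 1 change values per patient in Part A, Part B and Phase 2. That result needs no assumption about drug effect.

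The effect on the counts does depend on assumptions. With no acute effect it is at most about 0.6 patients in 40 above 30 msec, given the assumed SD of 6-10 msec. With an acute effect the counts would be too low, by an amount the documents cannot supply.

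Two further inferences should be avoided:

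- ECG chemistry does not become a QTc reference. It bears only on the laboratory percent-change listings.
- The loss should not be projected over later cycles as if the number of ECGs were settled. Attachment 1 marks an ECG on Day 1 of Cycle 2 onward but refers to Attachment 3 for details. Attachment 3 lists none after Cycle 2 Day 1 (Part A, Phase 2) or Cycle 1 Day 8 (Part B).

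Absolute QTc limits, listings of absolute values, site ECG review, the primary endpoint, power, the futility rule and DLT/MTD determination are unaffected.

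**What to change.** Replace the baseline entry in SAP Table JJCB.6.1 with:

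> Baseline is the last non-missing value before the first dose of study drug. Where a Cycle 1 Day 1 predose assessment is scheduled, use the predose record (for replicate ECGs, the mean of the predose replicates). Records taken after the first dose are not baseline.

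The replicate clause is needed because Protocol 10.3.2 collects ECGs as replicates, usually triplicates, and the present rule does not say whether the last replicate or their mean is used.

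The cost is one table entry and a small change to derivation code. No assessment is added, since Attachment 3 already schedules a predose ECG in every part. The case report form is not among the documents, so the sponsor should confirm that the data carry a predose/post-dose label or a time for each record.
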